## **7.9 Pharmacokinetic/Pharmacodynamic Analysis**

Not applicable.

### **7.9.1 Pharmacokinetic Analysis**

Not applicable.

### **7.9.2 Pharmacodynamic Analysis**

Not applicable.

## **7.10 Other Outcomes**

These are additional outcomes which will be summarized using the FAS analysis set and listed by subject.

They will need to be summarized only using descriptive statistics by 1) ENANTONE treatment phase, 2) Follow-up phase for those who were only treated with ENANTONE 3) Follow-up phase after completion of GnRHa therapy for those who were treated with ENANTONE and then another GnRHa after ENANTONE

- Evaluation of long term effect on reproduction which listed as following
  - Menstruation cycles (females)
  - Pelvic measurement
  - Male sexual characteristic examination
  - Hormonal measurements
  - $\beta$ -HCG (females)
  - Pregnancy

## **7.11 Safety Analysis**

Safety data will be summarized using the safety analysis set, and individual data will be presented in data listings. Safety outcomes will be analyzed by ENANTONE treatment (high, low dose and overall), and unless specified otherwise will not be stratified by sex. Separate summaries will be performed for the ENANTONE treatment phase and the different segments of the follow-up phase described in section 7.8.

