10.7.4 Safety Analysis

Safety outcomes will be analyzed by treatment (high, low dose) and overall, and unless specified otherwise, will not be stratified by sex. Separate summaries will be performed for the treatment phase and the follow up phase, both overall and at year intervals.

The primary safety outcome is the incidence per 100 person years (with 95% CIs) of AE and SAEs. All AEs and SAEs will be coded using the MedDRA coding dictionary. AEs and SAEs will be summarized together and separately at both MedDRA levels system organ class (SOC) and preferred term by tabulating the numbers of events, person years at risk and incidence per 100 person years. Furthermore, overall total number of events, person years at risk, and incidence per 100 person years (ie, any AE/SOC at any time) will be provided.

Incidence rates per 100 person years (95% CI) for polycystic ovarian syndrome will be determined for female subjects, by treatment group. Incidence rates per 100 person years for injection site reaction will be determined by treatment group.

If the data permit, changes in standard laboratory tests will be summarized using descriptive statistics.

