### **7.11.1 Adverse Events**

The primary safety outcome is the incidence per 100 person years of AEs and SAEs. All AEs and SAEs will be coded using the MedDRA coding dictionary. AEs and SAEs will be summarized together and separately at both MedDRA levels system organ class (SOC) and

preferred term by tabulating the numbers of events, the number of patient person years at risk and incidence per 100 person years (based on the numbers of events). Furthermore, overall total number of events, person years at risk, and incidence per 100 person years (ie, any AE/SOC at any time) will be provided.

The following AE subsets will be similarly tabulated. And system organ class and preferred terms will be sorted in decreasing frequency based on the number of subjects with adverse events in total, male, and female group:

- a) AEs related to ENANTONE treatment
- b) Most frequent AEs, all AEs with incidence of 3% or greater
- c) AEs/SAEs resulting in treatment discontinuation
- d) AEs by sex

All AEs will be presented in data listings.

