## **7.13 Changes in the Statistical Analysis Plan**

The statistical analysis in the protocol anticipated sufficient subject numbers to permit the comparing of Low and High dose levels of ENANTONE. At the time of finalizing the SAP it was determined that these types of analyses wouldn't be feasible. Therefore, the proposed Cochran-Mantel-Haenszel test will be omitted.

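### SAP 7.11 and 7.11.1 omit, without declaring it in 7.13, the protocol's yearly AE/SAE summaries and its dedicated injection-site-reaction rate

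*SAP*

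**What the plan says.** Protocol 10.7.4 (Safety Analysis) sets the time structure: "Separate summaries will be performed for the treatment phase and the follow up phase, both overall and at year intervals". It then adds a dedicated analysis: "Incidence rates per 100 person years for injection site reaction will be determined by treatment group".

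SAP 7.11 keeps the reporting by high dose, low dose and overall. Its sentence on time structure is "Separate summaries will be performed for the ENANTONE treatment phase and the different segments of the follow-up phase described in section 7.8". The segments, from SAP 7.8, are follow-up of ENANTONE recipients and, if data permit, the time during and the time after another GnRHa.

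SAP 7.11.1 gives rates by system organ class and "preferred term by tabulating the numbers of events, the number of patient person years at risk and incidence per 100 person years". It continues "The following AE subsets will be similarly tabulated" and lists four: AEs related to ENANTONE, AEs with an incidence of 3% or more, AEs or SAEs leading to discontinuation, and AEs by sex. None of these is injection-site reactions.

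SAP 7.13 says that comparing the dose levels was judged not feasible and concludes "Therefore, the proposed Cochran-Mantel-Haenszel test will be omitted". It says nothing about safety outputs.

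**The concern.** Safety is one of the two primary outcomes, and the study's purpose is to describe long-term use. SAP 7.7 tabulates treatment durations from 9 months to 60 months and beyond. A rate taken over a whole phase averages across that span. It describes the average correctly, but a reader cannot tell from it whether events occur mainly soon after the first injections or become more frequent with continued use.

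Injection-site reaction is the only AE given as an example in the primary safety outcome (protocol 10.2.1, SAP 5.1). The amendment table in protocol 6.0 explains that the separate injection-site outcome was removed because the primary safety outcome covers it. If the SAP then has no grouped injection-site analysis, nothing in the plan brings these events together.

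Both outputs disappear without a stated reason, so a reader comparing the report with the protocol could not tell a decision from an oversight.

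**Working it through.** The plan states no figure on this point, so the check is a comparison of texts. A short illustration on assumed inputs follows.

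**Step 1. The two safety sections side by side.**

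| Item | Protocol 10.7.4 | SAP 7.11 / 7.11.1 | Declared in SAP 7.13? |
|---|---|---|---|
| Rates by phase | Yes | Yes, with follow-up split into segments | Not applicable |
| Rates by dose group and overall | Yes | Yes | Not applicable |
| Rates by system organ class and preferred term | Yes | Yes | Not applicable |
| Summaries at year intervals | Yes | Absent | No |
| Dedicated injection-site-reaction rate by dose group | Yes | Absent | No |

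The polycystic ovarian syndrome rate, which stands next to the injection-site rate in protocol 10.7.4, is kept in SAP 7.8.3.

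**Step 2. Does another SAP section supply AE rates over time?**

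- SAP 7.1.3 sets 3-month windows for longitudinal data in both periods. Where a window holds several records, it keeps the one nearest the target day. That rule suits measurements. It does not say how to count events or divide person-time.
- SAP 7.1.7 mentions 3-month intervals for safety as well as efficacy, but only as the reason for a date-imputation rule. No table of AE rates by interval follows from it.
- SAP 7.1.5 imputes AE start dates solely to place an event before or after the first dose. A fully missing date becomes the first-dose date. A year-only date becomes the first-dose date or 1 January. If these defaults were reused for yearly tables, every undated event would fall in Year 1.

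So no section specifies an AE rate by year or by any other interval.

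**Step 3. What a whole-period rate can hide (all inputs assumed).** Crude rate = total events / total person-years × 100. Take 95, 60 and 30 person-years in Years 1, 2 and 3, total 185.

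- Early peak, 20/5/5 per 100 person-years: (19 + 3 + 1.5)/185 = 12.7.
- Late rise, 5/5/20: (4.75 + 3 + 6)/185 = 7.4.
- Constant, 10/10/10: (9.5 + 6 + 3)/185 = 10.0.

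With 95, 80 and 60 person-years (total 235) the three results are 11.1, 8.8 and 10.0. In both cases a four-fold late rise gives a lower crude rate than the early peak does. The crude rate does not identify the time pattern.

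**Step 4. What single-term rates can hide (all inputs assumed).** Suppose 6 of 100 children have one injection-site event each, over 185 person-years, coded to three preferred terms with 2 events each. The intervals are exact Poisson.

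- Grouped: 6/185 × 100 = 3.2 per 100 person-years (95% CI 1.2 to 7.1).
- Each term: 2/185 × 100 = 1.1 (0.1 to 3.9), shown three times.
- Each term affects 2% of children, below the 3% limit for the frequent-AE subset, while the group affects 6%.

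**The case against.** The strongest reply is that the SAP loses little. Every preferred term has events, person-years and a rate, by dose group and overall, so a reader who inferred that injection-site reactions get no rate at all would be wrong. It would also be wrong to infer that the SAP offers one crude average per phase: follow-up is split into segments, each phase or segment is reported by dose group, AEs are also tabulated by sex, and all AEs are listed. Both points stand. What is missing is the grouped injection-site rate and any breakdown by year. Whether the terms scatter in practice is unknown, because the documents list no coded events.

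A second reply is that SAP 7.1.7 shows that time-sliced safety data were contemplated. That is fair as far as it goes. It makes the SAP unclear about intervals for safety data, but it does not make AE rates by interval part of the plan.

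A third reply is that about 100 subjects, down from 300, make tables by year, dose and segment very sparse. This is a sound reason to limit the yearly tables to a few headline categories, or to drop them openly. It does not explain why 7.13 is silent.

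A reader might also infer that the omission creates a false dose difference. If both dose groups had 30 events per 100 person-years in Year 1 and 2 afterwards, 100 children treated for 1.5 years would give 31/150 = 20.7 per 100 person-years, and 100 treated for 3 years would give 34/300 = 11.3, a ratio of 1.8. The arithmetic is right, but the rates and durations are invented. The documents give no durations by dose group. The 2013 label change says nothing direct about how long each child was treated, and SAP 7.13 disclaims the dose comparison.

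**Conclusion.** The point holds as a departure of the SAP from the protocol. Two outputs that protocol 10.7.4 specifies for a primary outcome, yearly AE/SAE summaries in each phase and a dedicated injection-site rate by dose group, are absent from SAP 7.11 and 7.11.1 and are not declared in 7.13. The remaining rates are valid whole-period averages, but they cannot describe how AE risk changes over time, and injection-site events are rated only term by term.

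This conclusion rests on the text alone and needs no assumption. Its numerical effect cannot be stated. The figures in the working and the 1.8 ratio rest on assumed rates, person-years and coding; they show what could be hidden and are not evidence of size. The documents do not support saying that injection-site reactions go unrated or that a dose difference will be distorted. The matter should be corrected before analysis, but it does not undermine the safety analysis as a whole.

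**What to change.** 1. In SAP 7.11, tabulate AE and SAE events, person-years at risk and rate per 100 person-years for each phase overall and for Year 1, Year 2 and so on, by dose group and overall. At about 100 subjects it is reasonable to confine the yearly tables to any AE and any SAE. Split each child's person-time at the year boundaries and state the day from which follow-up years are counted.
2. Extend SAP 7.1.5 so that partly dated AEs can be assigned to a year, or show them on a separate undated line. Do not let the first-dose default decide the year. State whether the 3-month intervals in 7.1.3 and 7.1.7 apply to AEs.
3. In SAP 7.11.1, add one grouped injection-site-reaction rate over ENANTONE-treatment person-time, by dose group and overall, and list in advance the preferred terms that it combines.
4. If either analysis is dropped on purpose, declare it in SAP 7.13 with the reason.

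The cost is some SAP wording, a date rule and a few tables from data already collected. Many yearly cells will be sparse, especially by dose group and in later years, so each rate should be read beside its person-years.

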### **7.11.1 Adverse Events**

The primary safety outcome is the incidence per 100 person years of AEs and SAEs. All AEs and SAEs will be coded using the MedDRA coding dictionary. AEs and SAEs will be summarized together and separately at both MedDRA levels system organ class (SOC) and

preferred term by tabulating the numbers of events, the number of patient person years at risk and incidence per 100 person years (based on the numbers of events). Furthermore, overall total number of events, person years at risk, and incidence per 100 person years (ie, any AE/SOC at any time) will be provided.

The following AE subsets will be similarly tabulated. And system organ class and preferred terms will be sorted in decreasing frequency based on the number of subjects with adverse events in total, male, and female group:

- a) AEs related to ENANTONE treatment
- b) Most frequent AEs, all AEs with incidence of 3% or greater
- c) AEs/SAEs resulting in treatment discontinuation
- d) AEs by sex

All AEs will be presented in data listings.

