## 7.0 METHODS OF ANALYSIS AND PRESENTATION

### 7.1 General Principles

Statistical analysis will be performed using SAS® software (SAS Institute, Inc., Cary, North Carolina) Version 9.2, or later.

Data will be associated and summarized by the following:

- ENANTONE treatment phase includes all data from the first dose of ENANTONE up to and including either 45 days, inclusive, after the last dose or date of first dose of a non-ENTANTONE GnRH agonist therapy (earliest case scenario)
- Follow-up phase includes all data after the above defined ENANTONE treatment phase. If the subject continued treatment for CPP with another GnRH agonist after ENANTONE, their data from the follow-up period will be reported separately from those who only received ENANTONE for the treatment of CPP.

Unless specified otherwise, all data summaries will be performed for the following groups: Male, Female and Total, and will be presented during the ENANTONE treatment phase and results during the follow-up phase. Continuous variables will be summarized including the number, the mean, the standard deviation, median, minimum and maximum. Categorical variables will be summarized including the number and percentage of subjects.

Confidence intervals will be reported as 2-sided 95%, unless otherwise stated.

Means and medians will be presented to 1 more decimal place than the recorded data and standard deviations (SDs) will be presented to 2 more decimal places than the recorded data. Confidence intervals about a parameter estimate will be presented using the same number of decimal places as the parameter estimate. Derived variables may exhibit excessive decimal precision therefore, derived variables may be rounded to a precision representative of the expected data and means, SD and individual values will be formatted in a similar manner as described above.

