## **7.8 Efficacy Analysis**

Efficacy analyses will be performed on the FAS analysis set, and individual data will be listed.

Unless specified otherwise, only 95% confidence interval (CI) will be presented within sex group. No inferential analysis for comparison between sex group will be performed.

As described in section 7.1, efficacy results will be presented separately in the following segments by sex group (male and female plus total):

- Treatment Phase: ENANTONE treatment
- Follow-up Phase:
  - participants that received ENANTONE treatment in the treatment phase
  - If data permit, data from non-ENANTONE GnRHa treatment; as well as data after completion of non-ENANTONE GnRHa treatment

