### **7.8.1 Primary Efficacy Endpoint(s)**

The primary effectiveness outcome, percentage of subjects who have regression or no progression (i.e. response to treatment) in Tanner staging at the end of ENANTONE treatment (i.e. the last observation in the ENANTONE treatment phase) will be analyzed using an exact method. The 95% CI for the regression or no progression responder will be determined using Clopper-Pearson exact method. Similar analysis as described above will be performed at 3-month intervals from the initiation of ENANTONE treatment. Additional time intervals maybe utilized as fitting the data.

A Tanner Stage of 5 is satisfied when both evaluations for Tanner scoring are V; specifically, breast development and pubic hair for females and genital development and pubic hair for males.

Where applicable, similar summaries, using the appropriate baseline, will be presented for the follow-up phase at 3-month intervals.

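### SAP 7.11.1 restates the primary safety rate without the 95% CI that protocol 10.7.4 attaches to it, does not declare the change, and does not tie person-years at risk to the SAP 7.1 phases

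*SAP*

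**What the plan says.** **Protocol 10.7.4.** "The primary safety outcome is the incidence per 100 person years (with 95% CIs) of AE and SAEs". The same section asks for an interval on one further rate: "Incidence rates per 100 person years (95% CI) for polycystic ovarian syndrome will be determined for female subjects, by treatment group".

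**SAP 7.11.1.** "The primary safety outcome is the incidence per 100 person years of AEs and SAEs". The tabulation covers numbers of events, "the number of patient person years at risk and incidence per 100 person years (based on the numbers of events"). Every event counts, so one child can contribute several. No interval and no interval method is mentioned.

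**SAP statements about intervals elsewhere.** Section 7.1: "Confidence intervals will be reported as 2-sided 95%, unless otherwise stated". Section 7.8, on efficacy: "Unless specified otherwise, only 95% confidence interval (CI) will be presented within sex group". Section 7.8.1, for the other primary outcome: "The 95% CI for the regression or no progression responder will be determined using Clopper-Pearson exact method".

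**SAP 7.13.** It explains that comparing low and high dose is no longer feasible and concludes: "Therefore, the proposed Cochran-Mantel-Haenszel test will be omitted". It lists no other change.

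**Phases and time.** SAP 7.11 asks for separate safety summaries for the treatment phase and the follow-up segments described in 7.8, and 7.8 refers back to 7.1. Section 7.1 ends the treatment phase at the earlier of 45 days after the last ENANTONE dose and the first dose of another GnRHa. Follow-up is everything after that. The duration definitions are in 7.7 (Study Drug Exposure). There, follow-up for ENANTONE-only subjects starts at the last dose, and the treatment duration names the same two end points as 7.1 without saying that the earlier one applies.

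**The concern.** The protocol specified this interval in a study that it describes as descriptive and not powered for testing. In such a study the interval is the only statement of how much the data can exclude. Protocol 13.0 intends the results for the regulator. With about 100 children, SAE counts may be zero or very small, and a bare rate of zero can be read as absence of risk.

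The interval also needs a named method. The rate counts events rather than children, so a plain Poisson interval is too narrow if events recur in the same child.

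The denominator matters as well. If events were assigned by the 7.1 phases while time came from the 7.7 durations, the days just after the last dose would be counted in both periods and the follow-up rate would be diluted.

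**Working it through.** **1. Does any SAP text supply the missing interval?**
- 7.11.1 repeats the protocol's defining sentence minus the parenthesis on CIs.
- 7.1 fixes the level and sidedness of intervals that are reported. It does not say which estimates receive one.
- The 7.8 default does call for intervals, but it stands under efficacy and applies within sex group. Safety is in 7.11, by dose and overall, and is generally not stratified by sex.
- 7.13 gives infeasibility of the dose comparison as its reason. That does not bear on an interval for a single overall rate.

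So no SAP text supplies it for AEs and SAEs. The polycystic ovarian syndrome rate differs: 7.8.3 lists it among the additional efficacy endpoints, so the 7.8 default arguably covers it, and it needs only confirming.

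**2. What would the interval show?** The documents give no expected AE rate, event count, person-years or precision for safety, so there is no safety figure to reproduce. The only precision statement (protocol 10.5) concerns effectiveness. It does reproduce: 1.96 × √(p(1−p)/150) gives 6.93% at p = 0.75 and 5.71% at p = 0.85, against the stated 7% and 6%.

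For illustration, with x events in PY person-years, the exact Poisson limits per 100 person-years are
- lower = 100 × χ²(0.025; 2x) / (2·PY), taken as 0 if x = 0
- upper = 100 × χ²(0.975; 2x + 2) / (2·PY)

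For x = 0, χ²(0.975; 2)/2 = 3.689. Person-years below are assumptions; 75 is 100 children × the 9-month minimum.

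| Events | Person-years | Rate per 100 PY | 95% limits |
|---|---|---|---|
| 0 | 75 | 0 | 0 to 4.92 |
| 0 | 100 | 0 | 0 to 3.69 |
| 0 | 200 | 0 | 0 to 1.84 |
| 0 | 300 | 0 | 0 to 1.23 |
| 3 | 200 | 1.5 | 0.31 to 4.38 |

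**3. Does the method matter?** Simulation: 20,000 gamma-Poisson replicates, 100 children, 2 years each. The variance/mean ratio of the counts is an assumption. The robust interval uses Var(log rate) = Σ(yᵢ − rT)² / (Σyᵢ)² × n/(n−1), with t on 99 df. Here yᵢ is a child's event count, r the overall rate, T the 2 years and n the 100 children. Coverage of a nominal 95% interval at 20 expected events:

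| Variance/mean | Exact Poisson on events | Cluster-robust on log rate |
|---|---|---|
| 1 | 96% | 95% |
| 2 | 85% | 94% |
| 3 | 76% | 92% |

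At 3 expected events the robust interval appears to cover only 92%, 84% and 78% if zero-event replicates, which have no robust interval, count as misses. If those replicates receive the exact Poisson limit, coverage is about 97% at each ratio. At 10 expected events it is 96%, 93% and 91%. Coverage is therefore approximate at small counts, but the method is usable.

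**4. Person-time: 7.1 against 7.7.**
- Under 7.1 the first 45 days after the last dose belong to treatment. Under 7.7 they also open the ENANTONE-only follow-up. The maximum overlap is 45 × 100 / 365.25 = 12.3 person-years, if all 100 children are ENANTONE-only and observed for at least 45 days after the last dose. With 70 such children it is 45 × 70 / 365.25 = 8.6.
- If the 7.7 follow-up were the denominator for events assigned by 7.1, the follow-up rate would fall by 12.32 / (F + 12.32), where F is the 7.1 follow-up time: 11.0%, 5.8% or 3.9% at F = 100, 200 or 300 person-years.
- The missing word for the earlier date matters only for a child who starts another GnRHa more than 45 days after the last ENANTONE dose. For a start at day 90, 7.1 ends treatment at day 45, while the days-on-treatment text in 7.7 runs to day 90.

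**The case against.** **The CI was never withdrawn.** No SAP sentence removes it, and the protocol's own tabulation sentence also omits it. A reader might infer deliberate removal; the documents show only that the requirement was not carried over. But 7.13 is silent, 7.1 does not call for an interval here, and programmers work from the SAP. The gap stands whatever its origin.

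**The protocol names no interval method for rates.** True, so the missing method is not a departure from the protocol. It is something the SAP has to settle once the interval is restored.

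**The denominator can be traced.** Section 7.11 leads through 7.8 to the non-overlapping phases of 7.1, and nothing links 7.7 to 7.11.1. This largely stands. A reader might infer that follow-up rates will be diluted or the tail counted twice. The documents do not support that as a prediction; it happens only if 7.7 durations are used as person-years. What remains is the absence of an explicit sentence and a real conflict between 7.1 and 7.7.

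**Readers can compute intervals themselves.** Events and person-years are tabulated, so a plain Poisson interval, including a zero-event upper limit, is available. Allowing for repeat events would mean working back through the by-subject listings. That limits the harm but does not replace a planned interval on a primary outcome.

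**Small counts might seem to need a different measure.** A reader might infer from the 3-event coverage that sparse rows should switch to a first-event rate. The low coverage comes largely from treating zero-event replicates as misses. A first-event rate is also a different quantity, so it would not restore the interval that the protocol attached to the event rate.

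**Conclusion.** The point holds. The SAP omits, without declaring it, the 95% CI that the protocol makes part of the primary safety outcome. This rests on the text alone and needs no assumption. The sizes do rest on assumptions: an upper limit of 1.23 to 4.92 per 100 person-years behind a zero count (300 down to 75 person-years), and plain Poisson coverage of about 85% and 76% at 20 expected events with variance/mean 2 and 3.

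The person-years part is smaller. It is a missing explicit rule plus inconsistent duration text, worth at most 12.3 person-years, and it affects the rates only if 7.7 supplies the denominator.

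Two stronger readings are not supported. The protocol's tabulation sentence does not ask for intervals on system organ class or preferred term rows, so their absence there is no departure. Nor can the polycystic ovarian syndrome interval be called dropped, given the 7.8 default. Because the study is descriptive and no test depends on the interval, this should be corrected but does not invalidate the plan.

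**What to change.** 1. In SAP 7.11.1, restore the two-sided 95% CI on the overall AE and SAE event rates per 100 person-years, and confirm it for the polycystic ovarian syndrome rate in females. Use an interval on the event rate that allows for repeat events within a child, for example cluster-robust on the log rate, with the exact Poisson upper limit when there are no events. Note that coverage is approximate at small counts. Report the number of children with at least one event alongside. Intervals on system organ class and preferred term rows are not required. If the CI is deliberately dropped, declare and justify that in 7.13 instead.
2. Add one sentence stating that event assignment and person-years at risk for each phase both use the SAP 7.1 boundaries, without overlap. Reconcile 7.7 with 7.1 on the start of ENANTONE-only follow-up and on the earlier of the two treatment end dates.

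The cost is SAP wording and minor programming, with no new data. The intervals will be visibly wide, and the robust interval can still fall a few points below 95% when events concentrate in a few children.
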